6.0 Study Population

6.1 Inclusion and exclusion criteria (questionnaire outcomes)

Inclusion criteria

Diagnosis for asthma (confirmed by diagnostic Read code)

Age ≤65 years at index date for main outcomes, all ages for exploratory

Two years of continuous practice data comprising 2-year data prior to questionnaire

Asthma questionnaire returned

Prescription of Aerochamber[®] or Volumatic[®] spacer prior to the questionnaire

≥2 separate prescriptions of non extrafine beclomethasone in the baseline year prior to the index date

Exclusion criteria

Received multiple types of ICS or FDC ICS/LABA during the baseline period or at the index date

Prescribed both Aerochamber and Volumatic spacers

Table 6: Inclusion and exclusion criteria for questionnaire outcomes

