Patient-reported side effects will provide a unique perspective to disease outcomes compared to database Read codes, where bruising for example is seldom reported. An extract of the adult and child questionnaire is shown below (Figure 2 and Figure 3).

Do you experience any of these side effects from your preventer inhaler? Please tick yes or no for each one

	Yes	No		Yes	No
Continual sore mouth/throat			Hoarse voice		
Oral Thrush			Abnormal Weight Gain		
Bruising			Cough		

Figure 2: British Lung Foundation asthma questionnaire extract for adults

Does your child experience any of the following side effects from their preventer inhaler? Please tick Yes or No for each one

	Yes	No		Yes	No
Continual sore mouth or throat			Hoarse voice		
Oral thrush			Abnormal weight gain		
Bruising			Cough		

Figure 3: British Lung Foundation asthma questionnaire extract for children

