4.2 Study objectives

4.2.1 Primary objective

Non-inferiority of non-extrafine beclomethasone dipropionate with Aerochamber[®] spacer compared to non-extrafine beclomethasone dipropionate with Volumatic[®] spacer, in terms of the rate of patient-reported outcomes listed on the British Lung Foundation Questionnaire, ie the incidence of oral thrush or hoarseness.

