5.2 Study design (questionnaire outcomes)

A longitudinal study to compare patient-reported side effects for asthma patients prescribed non extra fine beclomethasone with Volumatic[®] spacer or Aerochamber[®] spacer (Figure 4). The index date of the study is the date of administration of the BLF Questionnaire. This study design will also be used to explore patients who step down at the index date with Volumatic and Aerochamber spacers. This exploratory objective will explore the baseline year (ie: year before index) in terms of comparative efficacy. If required (due to insufficient patients) an additional study design will be incorporated which will consider date of step down as index date (instead of date of BLF questionnaire).

[figure not shown]

Figure 4: Study Design (questionnaire outcomes)

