7.3 Questionnaire outcomes

Total and individual questionnaire related outcomes for

- 1) Continual sore mouth or throat
- 2) Oral thrush
- 3) Hoarse voice

* Calculated as average number of puffs per day over the year multiplied by strength (in µg);

[†] See appendix 1 for definitions

i.e. $\frac{\text{Number of inhalers} \times \text{doses per inhaler}}{365} * \text{strength}$

- 4) Bruising
- 5) Abnormal weight gain
- 6) Cough

As an exploratory outcome, the prescribed ICS dose at index dose will be considered to create the subgroups of step down patients for the Volumatic and Aerochamber spacers.

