8.4 Analysis of study outcomes

8.4.1 Primary analysis: Questionnaire based adverse events

Adverse events as total and individual events in the questionnaires will be compared using a conditional Poisson regression model. The model will use empirical standard errors and adjustments will be made for potential baseline confounders.

The adjusted rate ratio with 95% confidence interval will be reported.

Non-inferiority in patient reported adverse events (oral thrush OR hoarseness) will be achieved if the proportion of Clenil/Aerochamber is no more than 13% higher (based on the upper boundary of the 95% confidence interval) than the proportion of patients on Clenil/Volumatic.¹⁴

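### The questionnaire cohort does not require beclomethasone to be in use when side effects are asked about, so patients without current exposure can enter the non-inferiority test

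*Protocol*

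**What the plan says.** Protocol section 5.2 fixes the time point: "The index date of the study is the date of administration of the BLF Questionnaire". Section 6.1 sets exposure relative to that date. For the drug it requires "≥2 separate prescriptions of non extrafine beclomethasone in the baseline year prior to the index date". For the device it requires a prescription of either "spacer prior to the questionnaire", with no limit on how long before. The exclusion that mentions the index date reads "Received multiple types of ICS or FDC ICS/LABA during the baseline period or at the index date". It removes patients on several inhaled steroids or a fixed-dose combination, but not patients on none.

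The adult questionnaire extract in section 3.0 asks "Do you experience any of these side effects from your preventer inhaler", and the children's version is also in the present tense. Section 4.2.1 makes the primary objective non-inferiority of Aerochamber to Volumatic, "ie the incidence of oral thrush or hoarseness". Section 8.4.1 declares it when the Aerochamber proportion "is no more than 13% higher (based on the upper boundary of the 95% confidence interval").

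Dose at the index date appears only in section 7.3, for an exploratory purpose: "the prescribed ICS dose at index dose will be considered to create the subgroups of step down patients". By contrast, the database cohort in section 6.2 requires beclomethasone prescriptions after its index date.

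**The concern.** Exposure is defined over a year, while the outcome is taken at one moment at the end of it. A patient with two prescriptions 10 to 12 months before the questionnaire and none since meets every line of section 6.1. Such a patient may have no preventer in use and so can show no spacer effect.

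In a superiority comparison this would mainly cost power. In a non-inferiority comparison, diluting both arms equally shrinks the observed difference and makes the claim easier to reach. A patient who stopped because of thrush or hoarseness also remains in the denominator, quite possibly as a No. At stake is whether an excess of the size the plan regards as unacceptable could pass the test because some respondents were no longer exposed.

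**Working it through.** **Inputs from the protocol.** Section 8.1 gives a 0.300 proportion in the standard group, an expected difference of 0.000, a margin of 0.130, one-sided alpha 0.025, 80% power and groups of 293 and 147. The 13% in section 8.4.1 is read as percentage points, in line with section 8.1.

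**Assumed inputs.** f is the share of an arm that has stopped. b is the event rate that stoppers report, taken as 0 unless stated. The documents give neither.

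**Reproducing the plan's figure.** Use the unpooled normal approximation, with p_A and p_V the Aerochamber and Volumatic proportions:

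SE = √[p_A(1−p_A)/n_A + p_V(1−p_V)/n_V]

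P(declare NI) = Φ((0.13 − (p_A − p_V))/SE − 1.96)

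With both proportions 0.30 and 293/147, SE = 0.0463 and 0.13/SE = 2.807, so power = Φ(0.847) = 80.1%. The stated sizes reproduce and are not in dispute.

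**Equal stopping.** The observed proportion in an arm is (1−f)p + fb. With the same f and b in both arms, the difference becomes (1−f)d. Set current users at 0.30 on Volumatic and 0.43 on Aerochamber, so the excess sits exactly on the margin and the test should pass 2.5% of the time. With 293 Aerochamber, 147 Volumatic and b = 0:

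| f | p_A | p_V | Difference | SE | P(declare NI) |
|---|---|---|---|---|---|
| 0 | 0.430 | 0.300 | 0.130 | 0.0476 | 2.5% |
| 5% | 0.4085 | 0.285 | 0.1235 | 0.0470 | 3.4% |
| 10% | 0.387 | 0.270 | 0.117 | 0.0464 | 4.7% |
| 20% | 0.344 | 0.240 | 0.104 | 0.0448 | 8.4% |
| 30% | 0.301 | 0.210 | 0.091 | 0.0430 | 14.6% |

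Variations change little. At f = 20%, b = 10% gives 8.2%, swapping the arm sizes gives 8.1%, and doing both gives 7.9%. With 147 per arm, which is closer to the 1:1 matching of section 8.3, the results at f = 10%, 20% and 30% are 4.3%, 7.1% and 11.7%.

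**Unequal stopping.** Same true excess, b = 0, 293/147:

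- 10% stopped on Aerochamber, 20% on Volumatic: 0.43 × 0.90 − 0.30 × 0.80 = 0.387 − 0.240 = 0.147, and P(declare NI) is about 1.0%. The bias works against non-inferiority.
- 20% on Aerochamber, 10% on Volumatic: 0.43 × 0.80 − 0.30 × 0.90 = 0.344 − 0.270 = 0.074, and P(declare NI) is about 23%. The bias works for it.

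**Cost of restricting to current users.** With equal spacers at 0.30, removing 10% leaves about 264/132 and power of 75.9%. Removing 20% leaves about 234/118 and 70.9%. To retain 293/147 current users, 293/0.9 and 147/0.9 give 326/164 to be identified at f = 10%, and 293/0.8 and 147/0.8 give 367/184 at f = 20%.

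**The case against.** The strongest objection is about the target population. The study describes real-life use among patients who are prescribed the drug with a given spacer. If that is the intended population, an overall difference of 0.104 lies inside the margin and declaring non-inferiority is no error. The probabilities above are error rates only if current users are the target. This stands, and it is a reason to keep the existing cohort.

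A reader might infer that non-users certainly enter the analysis and certainly push the result towards non-inferiority. The documents do not support that. The criteria permit such patients without showing how many there are. The direction depends on how stopping splits between arms, as the 0.147 and 0.074 results show. Nor is a No from every stopper assured: someone without a preventer may leave the item blank, which is missing data and not dilution. A gap in prescriptions is not proof of stopping either, because intermittent users can stretch an inhaler.

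Cumulative beclomethasone and duration of ICS therapy are baseline variables (section 7.1), adjustment for confounders is planned (8.4.1), and matching on average ICS dose follows if numbers allow (8.3). These may balance low-exposure patients between arms, but they do not remove a dilution common to both.

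Restricting the primary set to current users would not be a clean cure. It removes the patients who stopped because of thrush or hoarseness and keeps those who tolerate the drug, which can also hide an excess. A days-of-supply rule would further need daily dosing instructions, which the average-dose formula attached to sections 5.3 and 5.5 does not use.

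Finally, a sensitivity analysis can be left to an SAP. Eligibility and the non-inferiority rule, however, are fixed in this protocol, and neither ties exposure to the questionnaire date.

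**Conclusion.** The gap is real. Followed exactly, section 6.1 can admit patients with no current beclomethasone exposure to a non-inferiority test on a present-tense outcome, and nothing else in the protocol closes it. If stopping is similar in the two arms and stoppers report no event, an excess at the margin among current users passes about 3.4%, 4.7% or 8.4% of the time at f = 5%, 10% or 20%, against the intended 2.5%. Those figures rest on assumed values of f, on b near zero and on current users being the population of interest. The documents establish neither the number of such patients nor the direction of the bias. The point therefore supports an added, decision-relevant analysis, not a replacement of the primary cohort.

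The effect on the step-down grouping in section 7.3 is minor and exploratory. A patient with no ICS dose at index has no stated place there. That such a patient would be counted as stepped down to nothing is a possible inference, but the text does not say so.

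**What to change.** Keep the section 6.1 cohort. In section 8.4.1, pre-specify:

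1. A current-user analysis limited to patients with a beclomethasone prescription within a fixed window before the questionnaire date. Define the window from prescription dates and pack size, and vary it in a sensitivity analysis.
2. A rule that non-inferiority is claimed only if the upper 95% limit lies within the margin in both the full cohort and the current-user set.
3. A table by arm of the number of patients without recent supply and their responses to the side-effect items, with blanks counted separately.

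In section 7.3, show patients with no ICS dose at index as a separate category.

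The work is small, because it uses prescription records and needs no patient contact. The price is power in the smaller set, about 76% at f = 10% and 71% at f = 20% without replacement, and requiring both sets to pass cannot give more than that. Counting patients without recent supply at extraction would show whether the numbers suffice. Both sets are needed because the current-user set alone can miss patients who stopped because of side effects, while the full cohort alone can be diluted.

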6.2 Inclusion and exclusion criteria (database outcomes)

Inclusion criteria

Diagnosis for asthma (confirmed by diagnostic Read code)

Age ≤65 years at index date for main outcomes, all ages for exploratory

4-years of continuous practice data comprising 1-year baseline data and 3-year outcome data

≥2 separate prescriptions of the beclomethasone pMDI in outcome year after index prescription date

Stepped down ICS in outcome period

Spacer prescription (Aerochamber or Volumatic)

Exclusion criteria

Received multiple types of ICS or FDC ICS/LABA during the baseline period, at the index date or during the outcome period

Prescribed both Aerochamber and Volumatic spacers

Table 7: Inclusion and exclusion criteria for database outcomes

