5.4 Study design (database outcomes)

This is a historical database study composed of a 1-year baseline period for demographics, characterisation and matching. The index date is the date of prescription of a spacer (Volumatic[®] or Aerochamber[®]), with a 3-year outcome period for detection of adverse events. Patients will require 4 years' continuous practice data.

[figure not shown]

Figure 5: Study Design (database outcomes) extractions from 2005 onwards

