5.5 Sub analysis

1. Characterisation of patients in terms of demographics, baseline variables and adverse events by age group (<16, 16–65, all ages, >65 as an exploratory group)
2. Characterisation of patients in terms of demographics, baseline variables and adverse events by prescription for high daily ICS dose (>500 μg fluticasone equivalence/1000 μg beclomethasone dipropionate) defined as ≥ 1 prescription for 1000 μg beclomethasone dipropionate during the baseline period
3. Characterisation of patients in terms of demographics, baseline variables and adverse events by high daily ICS dose (>500 μg fluticasone equivalence/1000 μg beclomethasone dipropionate) calculated as an average daily ICS dose[†] during the baseline period

* Average daily ICS dose will be calculated as: $\sum(((\text{Count of inhalers} * \text{doses in pack}) / \text{baseline period}) * \text{mcg strength})$

† Average daily ICS dose will be calculated as: $\sum(((\text{Count of inhalers} * \text{doses in pack}) / \text{baseline period}) * \text{mcg strength})$

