8.3 Matching

Initially, baseline data will be compared between unmatched cohorts. Exact matching for categorical variables and coarsened exact matching for numeric variables will be used to match patients using 1:1 nearest neighbour matching, without replacement. Matching variables such as demographic data, disease co-morbidity and indicators of disease severity will be considered for selection using a combination of baseline data analysis and predictive modelling of the baseline data in relation to the primary outcome variable (independently of treatment group).

If patient numbers allow, patients will be matched on sub groups for age (under 16s and 16-65 year olds) and high/low average ICS dose (1000 µg non-extrafine beclomethasone dipropionate or more/under 1000 µg non-extrafine beclomethasone dipropionate). For the sub-question of step down patients, matching will be implemented if the numbers are sufficient.

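### Database cohort: the dose strata are taken from a year in which beclomethasone is not required, so a patient with no prior inhaled steroid who starts it at or after the spacer is classed as low dose at any dose

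*Protocol*

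**What the plan says.** Four places in the Protocol have to be read together.

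- **Index date (5.4).** "The index date is the date of prescription of a spacer", Volumatic or Aerochamber. The study is "composed of a 1-year baseline period for demographics, characterisation and matching", followed by a 3-year outcome period.
- **Eligibility (6.2).** The beclomethasone criterion is "≥2 separate prescriptions of the beclomethasone pMDI in outcome year after index prescription date". Nothing requires beclomethasone, or any ICS, in the baseline year or on the index date. For the questionnaire cohort, 6.1 puts the requirement on the other side of index: "≥2 separate prescriptions of non extrafine beclomethasone in the baseline year prior to the index date".
- **Dose strata (5.5).** There are two definitions of high dose. One needs at least one "prescription for 1000 μg beclomethasone dipropionate during the baseline period". The other is "calculated as an average daily ICS dose" over the same period, by a formula that sums inhalers dispensed times doses per pack, divided by the baseline period, times strength.
- **Matching (8.3).** Where numbers are sufficient, patients are matched within subgroups that include "high/low average ICS dose", cut at 1000 µg. Section 8.3 names no time window. The baseline year is inferred from 5.4, which assigns matching to that year.

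Section 4.3 commits the secondary objective to a split by high and low dose. No rule is given for a patient without ICS in the baseline year.

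**The concern.** Cohort entry and dose classification use different periods. A patient can enter on post-index beclomethasone alone and then be classified by a year in which none was prescribed.

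Three consequences follow.

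- The low-dose stratum can mix genuine low-dose users with patients who start at any dose. The contrast in 4.3 then does not separate high from low steroid exposure.
- If dose matching is done, a patient starting a high dose can be paired with an established low-dose user on the other spacer and the pair counted as balanced. Steroid dose bears directly on the adverse reactions being counted, so this is a variable on which false balance matters.
- A patient given the spacer for a non-ICS inhaler, such as a reliever, who starts beclomethasone later contributes outcome time before any beclomethasone exposure. That time counts in the comparison of beclomethasone-plus-spacer groups.

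**Working it through.** **The plan's own figure.** The only design calculation is the 80% power in 8.1, which concerns the questionnaire analysis. With 293 and 147 patients, a proportion of 0.30 in both groups and a margin of 0.13, SE = √(0.30 × 0.70 × (1/293 + 1/147)) = 0.0463. Power is Φ(0.13/0.0463 − 1.96) = 80.1%. It reproduces, and nothing below changes it.

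**Step 1: ICS first started at or after index.** The 5.5 formula is

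average daily dose = Σ (inhalers × doses in pack ÷ baseline period) × strength.

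With no baseline inhalers this is 0 µg/day at each strength listed in 5.1 (50, 100, 200 and 250 µg), so the patient is below 1000 µg. There is also no 1000 µg prescription in the baseline period, so the prescription-based definition gives the same class. Both put the patient in the low stratum regardless of dose over the next three years.

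Counting the index day as baseline would not repair the averaging definition. One 250 µg inhaler, with 200 doses per pack assumed, gives 1 × 200 × 250 ÷ 365 = 137 µg/day. In any case, the ICS exclusion in 6.2 lists the index date separately from the baseline period.

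**Step 2: beclomethasone started shortly before index.** For a constant daily dose D begun m months before index, the baseline average is D × m/12. Doses and start times are illustrative assumptions.

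| Daily dose taken | 1 month | 3 months | 6 months | 9 months |
|---|---|---|---|---|
| 1000 µg | 83 | 250 | 500 | 750 |
| 2000 µg | 167 | 500 | 1000 | 1500 |

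A patient on 1000 µg/day is low dose by the average at every start time shown. One on 2000 µg/day needs 6 months of supply to reach 1000. In 250 µg inhalers of 200 doses (assumed), 7 in the year give 7 × 200 × 250 ÷ 365 = 959 µg/day and 8 give 1096, so eight are needed. This dilution belongs to the averaging definition only. Such a patient could be high dose under the prescription-based definition, so the two definitions can disagree.

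**Step 3: do the other 6.2 criteria remove these patients?**

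- The exclusion for multiple ICS types or fixed-dose ICS/LABA does not exclude someone with no ICS in the baseline year. It probably removes patients who switch to beclomethasone from another ICS.
- The criterion that ICS be stepped down in the outcome period states no reference dose. If it means a reduction from a baseline dose, it removes patients with no baseline ICS. As written, a patient who starts at index and steps down later satisfies it.

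**Step 4: unexposed outcome time.** If beclomethasone starts 3 to 10 months after the spacer (assumed), the unexposed share of the 36-month window is 3/36 = 8% to 10/36 = 28% for that patient. The documents give no distribution of delays.

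**The case against.** The strongest objection is the step-down criterion next to the quoted one in 6.2. If the reduction is measured from a baseline dose, patients with no baseline ICS never enter. Otherwise, starters enter only if they later reduce their dose, which narrows the group. This stands as a limit on certainty. It is not a rebuttal, because the reference dose is not stated and the wording admits a patient who starts at index.

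It is also fair to say that dose matching is conditional on patient numbers, and that its baseline timing is inferred. The 5.5 strata are neither conditional nor inferred.

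A reader might infer more than the documents support:

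- *That starting a high dose and a spacer together is the usual route into the cohort.* Section 3.0 says spacers are advised for adults on high doses. It does not say the two are started together, and it lists other reasons for a spacer. If most recipients already use beclomethasone, the effect could be negligible.
- *That the rate ratio is pulled towards 1.* That needs similar unexposed time and background risk in both arms. Table 2 shows Aerochamber licensed with several inhalers that do not fit Volumatic, so routes to a spacer may differ by arm. The direction is unknown.
- *That a patient could be matched to someone untreated.* Every cohort member needs at least two beclomethasone prescriptions after index, so a comparator can be untreated only in baseline or before a delayed start.
- *That a spacer prescribed for any other inhaler opens the route.* If the other inhaler is an ICS or ICS/LABA used in baseline, at index or in the outcome period, the exclusion should apply. Only a non-ICS inhaler fits.

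Finally, this is not detail to leave for an analysis plan. Index date, eligibility and dose strata are all fixed in this Protocol and do not fit together.

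**Conclusion.** The point holds for the secondary database analysis and its dose sub-analysis. For a patient with no ICS in the baseline year, the stated rules give 0 µg/day and the low stratum under both definitions, at any later dose. That is exact and needs no assumption. For a patient who starts shortly before index, the averaging definition understates the dose taken. The figures for that case rest on assumed doses, start times and pack size.

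The low stratum can thus contain high-dose starters, and dose matching, where applied, would not balance the dose actually taken. Some patients may also contribute outcome time before beclomethasone exposure. How many are affected cannot be derived from the Protocol, and neither can the direction of any bias. The conclusion assumes that the step-down criterion has no implied baseline reference. The primary non-inferiority analysis is not affected, because 6.1 requires beclomethasone in the year before the questionnaire. This should be corrected before extraction, but it does not threaten the main result.

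**What to change.** **Preferred.**

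- In 6.2, require a non-extrafine beclomethasone prescription on or before the spacer index date, same day allowed.
- In 5.5 and 8.3, take the dose stratum and the matching dose from the beclomethasone prescription current at index, and say how current is determined. Keep the baseline average as a descriptive variable.

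**Alternative.** Require at least two beclomethasone prescriptions in the baseline year, as 6.1 does. This removes the zero-dose patients but not, by itself, the dilution: two 250 µg inhalers of 200 doses (assumed) average 2 × 200 × 250 ÷ 365 = 274 µg/day.

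Under either option, state the reference dose for the step-down criterion in 6.2 and reconcile it with the dose used for the strata.

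**Cost.** Protocol wording and extraction code, with no new data. The preferred version loses some patients who start beclomethasone after the spacer, and the alternative loses all starters. A full redefinition of the index date with a further exact-matching variable is more than the problem needs and could cost matched pairs.

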4.2.2 Secondary objective

Comparison of database outcomes for non-extrafine beclomethasone dipropionate with Volumatic[®] spacer and non-extrafine beclomethasone dipropionate with Aerochamber[®] spacer in terms of Read codes for adverse reactions to beclomethasone dipropionate over a three-year period.

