8.4.2 Secondary analysis – database outcomes

The total number of adverse events as listed in the Summary of Product characteristics in the outcome period will be compared between treatment groups compared using a conditional

Poisson regression model. The model will use empirical standard errors and adjustments will be made for potential baseline confounders.

The adjusted rate ratio with 95% confidence interval will be reported.

Exploratory analysis – The exacerbation rate and separately the daily SABA dosage for patients during the baseline year who step down ICS at the index date treated with an Aerochamber spacer will be compared to patients prescribed a Volumatic spacer and compared with a Wilcoxon ranked test.

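### The database cohort admits only patients whose inhaled steroid was stepped down after the index date, so the secondary safety comparison is made in a subgroup selected during follow-up

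*Protocol*

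**What the plan says.** Section 6.2 of the protocol holds one table, captioned "Inclusion and exclusion criteria for database outcomes". Among its inclusion criteria is "Stepped down ICS in outcome period", with no indication that it applies to only part of the work. The age criterion in the same list is divided by purpose: "Age ≤65 years at index date for main outcomes, all ages for exploratory".

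Section 5.4 fixes the time frame: "The index date is the date of prescription of a spacer", "with a 3-year outcome period for detection of adverse events". The secondary objective (Section 4.2.2) compares the two spacers "in terms of Read codes for adverse reactions to beclomethasone dipropionate over a three-year period". Section 8.4.2 gives the analysis: "The total number of adverse events as listed in the Summary of Product characteristics in the outcome period will be compared between treatment groups".

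Step-down is treated elsewhere as an exploratory question (Section 4.2.3). Section 5.2 says the questionnaire design will be used to "explore patients who step down at the index date with Volumatic and Aerochamber spacers".

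**The concern.** A programmer who builds the cohort from the Section 6.2 table would discard every patient whose ICS was not stepped down in the three years after the spacer was prescribed. The secondary result would then describe patients whose dose was later reduced, not users of beclomethasone with each spacer.

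The selecting event also falls in the window in which the outcome is counted. Section 4.1 raises the possibility that Aerochamber improves efficacy and so leads to dose reduction, which makes step-down a possible effect of exposure. An adverse reaction to a steroid is also a plausible reason to reduce its dose. Selecting on a variable that both exposure and outcome can influence is collider selection. It can create or hide a difference between spacers, and the matching and adjustment in Sections 8.3 and 8.4.2 use baseline variables only, so they do not remove it.

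**Working it through.** **The protocol's own figure.** The only stated power is for the primary questionnaire comparison (Section 8.1): groups of 293 and 147, event proportion 0.30, true difference 0, margin 0.13, one-sided 0.025. The standard error is √[0.30 × 0.70 × (1/293 + 1/147)] = 0.0463. Power is Φ(0.13/0.0463 − 1.96) = 0.801, which matches the stated 80%. It does not depend on the disputed criterion. No sample size or power is given for the database comparison, so there is nothing to recompute there.

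**Sections side by side.**

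| Section | Role of step-down | Timing of step-down |
|---|---|---|
| 4.2.2, 5.4 and the secondary analysis in 8.4.2 | none | – |
| 4.2.3, 7.5 | defines an exploratory group; outcomes are baseline exacerbations and SABA use | – |
| 5.2 | exploratory, questionnaire design | at index; in the fallback, step-down is itself the index |
| 7.3 | exploratory subgroups formed from the dose at index | at index |
| Exploratory paragraph of 8.4.2 | baseline-year comparison | at index |
| 6.2 | inclusion criterion for the database cohort | during the outcome period |

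No analysis described in the protocol uses step-down during an outcome period that follows a spacer prescription. Two further places imply that step-down patients are a subset: Section 8.3 matches them only if numbers suffice, and the last mock table in Appendix 2 has columns for patients with and without step-down.

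**Loss of patients.** The share stepping down in three years is not given. If it is 10% to 30% (assumption), the criterion removes 90% to 70%.

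**Possible distortion of the ratio.** Let *p* be the adverse-event risk in an arm, and *s*₁ and *s*₀ the probabilities of step-down with and without an event. Among step-down patients the risk is

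p·s₁ / [p·s₁ + (1 − p)·s₀].

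All values of *s* are assumptions. The risk of 0.30 is borrowed from the questionnaire power calculation and is not a database rate. A is Aerochamber, V is Volumatic.

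| True risks A, V (ratio) | s₀/s₁ in A | s₀/s₁ in V | Selected risk A | Selected risk V | Ratio seen |
|---|---|---|---|---|---|
| 0.30, 0.30 (1.00) | 0.30/0.30 | 0.20/0.20 | 0.300 | 0.300 | 1.00 |
| 0.30, 0.30 (1.00) | 0.20/0.30 | 0.20/0.30 | 0.391 | 0.391 | 1.00 |
| 0.30, 0.30 (1.00) | 0.25/0.30 | 0.20/0.30 | 0.340 | 0.391 | 0.87 |
| 0.30, 0.30 (1.00) | 0.30/0.30 | 0.20/0.30 | 0.300 | 0.391 | 0.77 |
| 0.30, 0.30 (1.00) | 0.30/0.30 | 0.15/0.30 | 0.300 | 0.462 | 0.65 |
| 0.40, 0.30 (1.33) | 0.30/0.30 | 0.20/0.30 | 0.400 | 0.391 | 1.02 |

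For the fourth row: A is 0.09/(0.09 + 0.21) = 0.300, V is 0.09/(0.09 + 0.14) = 0.391, and the ratio is 0.77. The first two rows show when a null ratio survives: step-down is unrelated to events, or related to them identically in both arms. The last row shows a real excess disappearing. Reversing the assumed patterns between spacers would reverse the direction of the error.

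**The case against.** The strongest reply is that this is a labelling slip: the line was meant for the step-down sub-question and reached the main list without a qualifier. The columns for patients without step-down in Appendix 2 support that reading, and the exploratory step-down paragraph sits under the database heading of Section 8.4.2 without naming the questionnaire design. This may well be how the line arose, but it does not rescue the text. That same paragraph places step-down at the index date, as Section 5.2 does, so a criterion requiring it in the outcome period fits neither the sub-question nor its fallback. The questionnaire criteria in Section 6.1, where Section 5.2 places the sub-question, contain no step-down line.

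It is also fair to say that bias is conditional. The protocol says nothing about adverse events prompting step-down; that link is an inference. The step-down probabilities and the 10–30% share have no anchor in the document. These points limit what can be said about the size of any bias. They do not touch the restriction of the population.

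Finally, the same table imposes other post-index conditions: at least two beclomethasone prescriptions in the outcome year, and no other ICS or ICS/LABA combination during the outcome period. That is true, and deleting the step-down line leaves them in place, but it is a separate matter and no reason to keep this one.

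**Conclusion.** The concern holds. As written, Section 6.2 contradicts Sections 4.2.2, 5.4 and 8.4.2 and restricts the whole secondary safety comparison to patients selected on a post-index event. That change of population follows from the protocol's own definitions and needs no assumption. How many patients would be lost, and how far the rate ratio would move, cannot be determined from the document; the figures above illustrate what could happen and are not estimates. The primary non-inferiority analysis uses the questionnaire cohort and is not affected. Because one line redefines the cohort for an entire objective, it must be corrected before data are extracted.

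**What to change.** Delete the step-down line from the inclusion criteria in Section 6.2, so that the database cohort matches the secondary objective. If the fallback in Section 5.2, with step-down as the index date, is used, give it a separate eligibility list that states when step-down must occur and in which data source. The cost is one line in one table before extraction. No new data are needed, and the database cohort becomes larger.
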